3.2.8 Study design

A stepped-wedge cluster randomized trial design will be used to evaluate the impact of the intervention. Using this design, the intervention will be implemented sequentially to the participating hospitals over 6-month time periods (Table 2). The period at which a hospital begins implementation of the intervention (or enters the “active phase” of the study) will be determined at random. The intervention will be applied at the level of the hospital (clusters). Participating hospitals will be randomized to one of four wedges, giving around 24 hospitals per wedge. Wedge

randomization will be computer-generated. The survivors will be followed up at 6 months and 12 months.

Table 2 Patient Selection and Intervention Plan

	0-6 month	7-12 month	13-18 month	19-24 month	25-30 month
A group (24 hospitals)	A0 (baseline)	A1 (intervention)	A2 (intervention)	A3 (intervention)	A4 (intervention)
B group (24 hospitals)	B0 (baseline)	B1 (baseline)	B2 (intervention)	B3 (intervention)	B4 (intervention)
C group (24 hospitals)	C0 (baseline)	C1 (baseline)	C2 (baseline)	C3 (intervention)	C4 (intervention)
D group (24 hospitals)	D0 (baseline)	D1 (baseline)	D2 (baseline)	D3 (baseline)	D4 (intervention)

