3.2.10 Sample Size

Sample size calculations are based on following assumptions:

- The baseline incidence rate of in-hospital major adverse cardiovascular events (MACE) is assumed as 8.4%. This parameter came previous findings from CPACS-1 (8.4%) and CPACS-2 studies (7.6%). Taking into account that participating hospitals in CPACS-3 come from remote areas with limited medical resources, a higher incidence of MACE in CPACS-1 is used to calculate the sample size;
- no delay in the effect of the intervention;
- an intra-class correlation coefficient of 0.10 (data from CPACS-2 study);
- 96 participating hospitals, 50 patients will be collected in each 6-month cycle in each hospital, and the intervention will be started in four steps;
- We select 4 hospitals from each province in Jiangsu Province, Guangdong Province, Gansu Province, Sichuan Province, Guizhou Province, and Inner Mongolia Autonomous Region and select 8 hospitals from each of the

remaining 9 provinces: Hebei Province, Liaoning Province, Jilin Province, Anhui Province, Shandong Province, Shanxi Province, Henan Province, Hubei Province, and Shaanxi Province.

This study will have 99%, 98% and 85% power to detect relative risk reduction of 25%, 20% and 15% respectively in the primary outcome (Table 3).

Table 3 Statistical power of CPACS-3

Relatively risk decline	Statistical power
25%	99%
20%	98%
15%	85%

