3.3 Quality control

Each hospital will receive training of the research protocol before the start of the project and will receive the training on intervention protocol before the commencement of the intervention.

After the research protocol training but prior to the formal data entry a period of one month is blocked for practice. During this period, the data entry staff will be checked if he/she is qualified by examining whether the data inputted into the CPACS-3 IT system are matched with the medical charts separately sent to the coordinating center. After the qualification validated, the participating hospital could begin its formal recruitment.

Each participating hospital will receive the site monitoring visit at least twice, one within half a year after initiating the study and one within the last year before the end of the study. There is no difference in the time of the first monitoring visits. In the first six months of the project (February-June), the first monitoring visits of all 96 centers will be completed; the second monitoring visits will be done in 2-3 times. 20% to 40% of 96 centers will be checked at each time, and the second monitoring visits will be completed within one and a half years. Routine data queries will be conducted through the data management center.

The site monitoring visits should check the establishment and operation of the QCI team, documentation and filing, patient ID verification, original data sourcing, the implementation of clinical pathway, etc.

The site monitoring results will be reported back to the hospital QCI team as well as the project team, the corresponding local health bureaus and the Ministry of Health. The project team may raise critics and appraisals to the participating hospital on the basis of the monitoring results. The project team can withdraw hospitals that are seriously unqualified for data authenticity and data quality.

4. Statistical analysis plan

As the stepped-wedge cluster randomized trial design, we plan to analyse the study data at individual level. Considering that the response variables may be non-normal distribution or binomial distribution, and the sizes of the clusters may be unequal, we plan to use the generalized linear mixed models (GLMM) or generalized estimating equations (GEE) to do statistical analyses.

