4.1 Effectiveness evaluation

For the primary end point (binary variable, in hospital major adverse cardiovascular events (MACE), including stroke, AMI, hospital readmission, vascular reconstruction and all-cause mortality), GLMM model will be used to evaluate the treatment effect (between intervention groups) and the time effect (between different patients in different time periods), with LOGIT/POSSION conversion of the end point. If there is neither the time effect nor the interaction term between time and intervention, the COX model or LOGISTIC regression model will be used to estimate the intervention effect after adjustment of covariates.

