4.2 Basic situation evaluation

GLMM model will also be used to compare the socio-anthropometric variables between the intervention groups, and between time periods, as well as between patients with different discharge diagnosis (STEMI, NSTEMI, UAP). If there is neither the time effect nor the interaction with the intervention, *t* test will be used to compare the difference of continuous variables between the intervention groups.

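### The fallback in Section 4.1 drops hospital and period terms when no time effect is found; at the protocol's ICC of 0.10 this gives about a 40% false-positive rate for the primary outcome.

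*Protocol*

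**What the plan says.** The opening of Section 4 recognises the clustered design: "we plan to use the generalized linear mixed models (GLMM) or generalized estimating equations (GEE) to do statistical analyses". Section 4.1 then specifies, for in-hospital MACE, a GLMM with a treatment effect and a time effect, followed by a conditional replacement: "If there is neither the time effect nor the interaction term between time and intervention, the COX model or LOGISTIC regression model" estimates the intervention effect, adjusted for covariates that are not named. Section 4.2 has a parallel rule for patient characteristics: under the same condition, a t "test will be used to compare the difference of continuous variables between the intervention groups". Section 4.3, on the secondary outcomes, uses the GLMM with no such exit.

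Neither fallback mentions hospital, a random effect, a frailty or a robust variance. Yet Section 3.2.10 sizes the trial on "an intra-class correlation coefficient of 0.10 (data from CPACS-2 study").

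**The concern.** The rule makes two separate mistakes.

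1. **Clustering.** Patients in the same hospital are correlated whether or not event rates drift over time. A test for time is therefore no evidence that an ordinary logistic or Cox model is adequate. Treating 24,000 patients as independent when they come from 96 randomised hospitals gives standard errors that are too small.
2. **Time.** The staggered roll-out in Table 2 ties intervention to calendar time. A non-significant test does not show that there is no trend, and any trend it misses is credited to the intervention once the period terms are removed.

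The condition is met in most trials that have no trend, so the fallback would often be the analysis actually reported for the primary outcome. At stake is the trial's main conclusion.

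**Working it through.** **Inputs**

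- Section 3.2.10: "96 participating hospitals, 50 patients will be collected in each 6-month cycle in each hospital, and the intervention will be started in four steps". This gives 5 periods and 96 × 5 × 50 = 24,000 patients.
- Section 3.2.8: "Participating hospitals will be randomized to one of four wedges, giving around 24 hospitals per wedge". By Table 2, groups A to D have 4, 3, 2 and 1 intervention periods out of 5. That is 240 intervention and 240 control hospital-periods, or 12,000 patients each.
- Section 3.2.10: "The baseline incidence rate of in-hospital major adverse cardiovascular events (MACE) is assumed as 8.4"%; ICC 0.10.
- Assumed, because the protocol gives none: two-sided 5% for the treatment test and for the preliminary tests; the ICC read on the proportion scale and applied to MACE.

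The protocol states no false-positive rate, so there is no figure of its own to reproduce. Its power figures are a separate matter and are not used here.

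**Standard error of the unclustered contrast** (units of total outcome variance)

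- Intervention minus control periods per hospital: +3, +1, −1, −3 for groups A to D.
- Weight on hospital variance: c = 24 × (9 + 1 + 1 + 9) / 240² = 480 / 57,600 = 0.00833.
- True variance: ICC × c + (1 − ICC) × 2/12,000 = 0.10 × 0.00833 + 0.90 × 0.000167 = 0.000983.
- Variance assumed by an unclustered model: 2/12,000 = 0.000167.
- Ratio: 0.000983 / 0.000167 = 5.9, which here equals 1 + 49 × ICC. The SE is too small by √5.9 = 2.43.
- Rejection rate under the null: 2 × [1 − Φ(1.96/2.43)] = **42%**.

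| ICC | Variance ratio | Nominal 5% test rejects |
|---|---|---|
| 0.01 | 1.49 | 11% |
| 0.02 | 1.98 | 16% |
| 0.03 | 2.47 | 21% |
| 0.05 | 3.45 | 29% |
| 0.10 | 5.90 | 42% |

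**The whole two-stage rule, simulated.** Hospital rates were beta-distributed and there was no intervention effect. A 4-df period test and a 1-df time-by-intervention test were each done at 5%. If both were non-significant the unclustered analysis was used; otherwise the hospital-plus-period model was used.

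- No trend, ICC 0.10: fallback used in about 90% of trials; error given the fallback 42%; error of the whole rule 39% to 40%.
- No trend, ICC 0.03: whole rule about 21%. ICC 0.01: about 11%.
- Hospital and period always kept, ICC 0.10: 4.4% to 5.4%, with trends from 0 to −5% per period.

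**Undetected trend.** The mean period of intervention cells is (24×2 + 48×3 + 72×4 + 96×5)/240 = 4.0. For control cells it is (96×1 + 72×2 + 48×3 + 24×4)/240 = 2.0. The gap is two periods, or 12 months. For illustration, suppose rates fall by 5% per 6 months for reasons unrelated to the intervention. The crude risk ratio is then about 0.95² = 0.90. In simulation at ICC 0.10 the fallback is still chosen in 65% to 67% of such trials, and the mean risk ratio it reports is 0.90 to 0.91 with no true effect. Error given the fallback is then about 57%.

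**The case against.** The strongest reply is that the protocol never says clustering is abandoned. The covariates are unnamed, Section 4 opens with GLMM or GEE, and a logistic model fitted by GEE is still a logistic model. However, Section 4.1 presents the Cox or logistic model as the alternative to the GLMM, and the parallel alternative in Section 4.2 is a t test, which cannot carry a hospital term. The plain reading is that hospital is dropped. If the sponsor intends otherwise, the sentence still has to be corrected.

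The second reply concerns the size, and part of it stands. The protocol does not say which outcome or scale its ICC refers to. On the proportion scale, 0.10 with a mean of 8.4% implies a between-hospital SD of about 8.8 percentage points, which is large. If 0.10 is instead on the latent logit scale, the proportion-scale ICC is about 0.03 and the error about 21%. The preliminary tests and their 5% level are also assumptions. These points move the answer within the tabulated range; none brings it near 5%.

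Third, with no secular trend nearly all of the inflation comes from losing the hospital term; losing period matters when a trend exists and is missed. The 5% fall per period is an illustration, not a figure from the protocol. Fourth, Section 4.2 compares patient characteristics, and the protocol gives no ICC for them, so the 40% cannot be attached to it. Both points are accepted.

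**Conclusion.** The concern holds. Read plainly, Section 4.1 prescribes an invalid analysis of the primary outcome in the situation where it is most likely to be triggered. At ICC 0.10 on the proportion scale and a two-sided 5% level, type I error is about 42% when the fallback is used and about 40% for the rule as a whole. Over ICCs of 0.01 to 0.10 the fallback's error runs from 11% to 42%, always at least twice nominal. Where a secular decline is missed, the estimate is biased towards benefit as well. Section 4.2 contains the same error of method, with less at stake and no error rate that can be computed from the protocol. This should be corrected before analysis.

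**What to change.** - In Section 4.1, delete the conditional sentence. State that the primary model always contains fixed period effects and a hospital random effect, whatever their p-values. A hospital-by-period random effect is a sensible addition but is not needed to cure this defect.
- In Section 4.2, delete the t-test sentence and use the same clustered, period-adjusted model.

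No patients, data or visits are added. The cost is a wider confidence interval, which is the correct one. The sponsor should also know what the retained model implies for power. With a random hospital intercept, fixed periods, ICC 0.10 and a two-sided 5% test, power for relative reductions of 25%, 20% and 15% comes to about 93%, 78% and 54%. Section 3.2.10 states: "This study will have 99%, 98% and 85% power to detect relative risk reduction of 25%, 20% and 15% respectively in the primary outcome". That gap needs its own review, but it is not a reason to keep the fallback.

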recommend four drugs (aspirin, beta-blockers, ACEI/ARB and statin) was 61.6% and 51.2% respectively (OR 1.42; 95% CI: 1.00-2.02; $p=0.061$); with the implementation of intervention, the hospital stay was significantly reduced ($p=0.001$) and the proportion of patients treated with the four drugs also significantly increased ($p=0.004$). Other indicators, such as the proportion of STEMI with reperfusion therapy, the door-to-needle time and door-to-balloon time also showed a trend of improvement, but not statistically significant. The incidence of major adverse events (including death, myocardial infarction, and stroke) in the hospital decreased, but which was only significant before controlling potential confounders ($p=0.009$).

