10	Reperfusion therapy for STEMI patients	Proportion of STEMI patients who arrive hospital within 12 hours of symptom onset receiving fibrinolysis
11	Door to needle time	Proportion of AMI patients with ST-segment elevation or LBBB on the ECG closest to hospital arrival time receiving fibrinolytic therapy within 30 min from arrival to the hospital.
12	Length of stay	Mean days of hospitalization
13	Diagnosis inconsistent with examination findings	Proportion of patients with a final diagnosis inconsistent with biomarker findings

Patient satisfaction survey will focus on the experiences that the patient just went through in seeking the medical care, in order to determine the patient satisfaction level. We will ask about the reasons for patients’ dissatisfaction and the possible factors related to patient satisfaction including hygiene level of the ward, quietness

at night, communication satisfaction with nurses and doctors, timely responsive in case of problems, accessibility to the necessary information at discharge, overall satisfaction score and whether willing to recommend this hospital to others. The questionnaire will first be validated in a small group of people and to be used after proving its validity.

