3.2.9 Outcomes

The primary outcome will be the incidence rate of in-hospital major adverse cardiovascular events (MACE) comprising all-cause mortality, myocardial infarction or re-infarction and stroke. Secondary outcomes will be the key performance indicators (KPIs) and the patient satisfaction.

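### The section 4.1 fallback allows a Cox model in place of logistic regression for a binary in-hospital endpoint, and the two can disagree if the intervention changes length of stay

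*Protocol*

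**What the plan says.** Protocol section 3.2.9 defines the endpoint as an incidence: "The primary outcome will be the incidence rate of in-hospital major adverse cardiovascular events (MACE"), made up of death, infarction or re-infarction, and stroke. Section 4.1 gives its type: "For the primary end point (binary variable, in hospital major adverse cardiovascular events (MACE"). The main analysis there is a GLMM with intervention and time effects and a logit or Poisson link.

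A fallback follows. Its condition is "If there is neither the time effect nor the interaction term between time and intervention"; when that is met, "the COX model or LOGISTIC regression model will be used to estimate the intervention effect after adjustment of covariates". The protocol does not say which of the two models applies. For the Cox option it gives no time origin, censoring rule, common horizon or treatment of discharge.

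Two other places bear on this. Length of stay is KPI 12 in Table 1 of section 3.2.6 ("Mean days of hospitalization"), and under section 3.2.7 the KPIs are fed back to hospitals every six months. For the predecessor trial, section 2.3 reports that with implementation "the hospital stay was significantly reduced ($p=0.001"). It does not give the size of the reduction.

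**The concern.** For a binary in-hospital endpoint, logistic regression tests whether the proportion of patients with a MACE before discharge is the same under control and intervention. A Cox model in its usual form needs a follow-up time for every patient. For a patient without an event, in-hospital observation stops at live discharge, so the usual coding censors there. The null is then an equal hazard per day still in hospital.

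The two nulls agree when length of stay is the same under both conditions, but this intervention audits stay and its predecessor shortened it. If stay changes, two analysts who both follow the fallback sentence could report different conclusions on the primary endpoint from the same data.

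**Working it through.** **Inputs from the protocol.** Sections 3.2.8 and 3.2.10 give 96 hospitals × 50 patients × 5 periods = 24,000 patients. Table 2 has 1+2+3+4 = 10 control and 10 intervention group-periods of 24 × 50 = 1,200 patients, so 12,000 per condition. Section 3.2.10 states "The baseline incidence rate of in-hospital major adverse cardiovascular events (MACE) is assumed as 8.4"%, which gives 24,000 × 0.084 = 2,016 events at equal incidence. It also gives "an intra-class correlation coefficient of 0.10 (data from CPACS-2 study"). No figure in the protocol concerns the fallback, so there is none to reproduce; the power figures in Table 3 do not enter.

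**Inputs assumed.** Two-sided 5% test; gamma length of stay with mean 10 days; stay cut by 5%, 10% or 20% under intervention; several patterns of event timing. The documents give none of these.

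**Mechanism.** Suppose *d* events occur on a given day under each condition, with R₀ control and R₁ intervention patients still in hospital. The Cox contribution that day is (d/R₁)/(d/R₀) = R₀/R₁. If event-free patients go home sooner under intervention, R₁ < R₀ and the ratio exceeds 1, although the event counts are equal.

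**Case 1: a shorter stay changes no event (incidence 8.4% in both conditions).** Rejection rates of Cox with discharge censored:

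| Event timing | Stay 10% shorter | Stay 20% shorter |
|---|---|---|
| Exponential, parameter 2-5 days, bounded by the patient's stay (no clustering) | about 5-12% | about 10-41% |
| Uniform over the stay (no clustering) | about 44% | about 98% |
| Uniform over the stay, stepped-wedge layout, ICC 0.10, Cox stratified by hospital | 30% (HR 1.07) | 87% (HR 1.17) |

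The binary test stays near 5% throughout. Where rejection is clearly inflated, almost all of it is towards harm. The third row shows that accounting for hospital does not remove the problem. I repeated the unclustered rows with 1,000 runs per setting and gamma shape 4. The results were 6-13% and 11-43% for bounded exponential times, and 40% and 97% for uniform times, so the unclustered figures are good to a few points. With a 5% shorter stay and bounded exponential times, the repeat gave 5-6%, which is negligible. With no change in stay, Cox rejected at about the nominal rate.

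**Check by formula.** With 2,016 events split 1:1, z = ln(HR) × √2016 / 2 = 22.45 × ln(HR), and the rejection probability is about Φ(z − 1.96).
- HR 1.05: z = 1.10, 19%
- HR 1.10: z = 2.14, 57%
- HR 1.15: z = 3.14, 88%

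With this many events, even a small spurious hazard ratio matters.

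**Case 2: the daily in-hospital hazard is unchanged and stay is 10% shorter.** Incidence falls to about 8.4% × 0.9 = 7.6%. For the binary comparison, SE = √[(0.084×0.916 + 0.076×0.924)/12,000] = 0.0035 and z = 0.008/0.0035 = 2.28, so it rejects with probability Φ(2.28 − 1.96) = 63%. In simulation Cox gives HR 1.00 and rejects in 3% of runs.

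**Case 3: stay 10% longer, incidence equal (uniform events, clustered).** Cox gives HR 0.94 and rejects in 26% of runs, nearly all towards benefit.

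**The case against.** The strongest replies are these.

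- *The route is conditional and optional.* This stands. The GLMM is the main model. Cox enters only if no time effect or interaction is found, and then only as an alternative to logistic regression. A reader might infer that the primary analysis as a whole is unsound; the protocol does not support that.
- *Discharge need not be censored.* This also stands. A reader might infer that censoring is the only way discharge can enter a Cox model. A subdistribution model, or carrying event-free patients to a common horizon, would avoid the problem. A statistical analysis plan that is not shown could specify one. The protocol names neither, and it is the protocol that pairs this model with a binary endpoint.
- *The error need not run towards harm.* Correct. That direction requires that a shorter stay leaves every event unchanged. Case 2 shows Cox missing a fall in incidence, and in Case 3 the error runs towards benefit.
- *The binary analysis depends on stay too.* Correct. In Case 2 the fall in incidence arises because patients are observed for fewer days. This is a reason to show length of stay beside the result. It does not favour Cox, which targets a quantity that section 3.2.9 does not define.
- *Cox may have been meant for follow-up events.* The component list in section 4.1 includes readmission and revascularisation, which resemble the follow-up events in section 3.2.5. But the same sentence calls the endpoint binary and in-hospital, and section 3.2.9 lists neither component. That mismatch is a separate point to reconcile.
- *The size could be overstated.* It can be. Event times drawn without regard to stay give much higher rates: 46% and 99% for a 5-day mean with stay 10% and 20% shorter. Those runs place events later than many patients would have been in hospital, so they should not be relied on.

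**Conclusion.** The point holds in limited form. The fallback in section 4.1 offers two models as alternatives although they estimate different quantities, and only the logistic one matches the defined endpoint. They can disagree if the intervention changes length of stay, and the protocol itself gives reason to expect that it may.

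The size is uncertain, because the protocol gives no length of stay, no size of reduction and no event timing. At equal incidence the inflation runs from negligible (early events, small change in stay), through 10-41% (stay 20% shorter, bounded exponential times), to nearly certain rejection (stay 20% shorter, events uniform over the stay). The direction depends on how stay and events move together. The main GLMM analysis is unaffected. The change should be made, but the point does not undermine the design.

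**What to change.** Delete the Cox option from section 4.1. Analyse in-hospital MACE only as a binary variable, with the logit GLMM already named, and keep the hospital effect in any simplified version. If a time-to-event display is wanted, make it supportive and treat live discharge as a competing event (cumulative incidence, or Fine-Gray). Report length of stay by condition beside the primary result, because the observation window of the binary endpoint also depends on stay.

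The cost is a small wording change and one descriptive table. Length of stay is already collected as KPI 12, so no new data, patients or procedures are needed. All that is given up is an optional hazard ratio that the defined endpoint does not need.
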